3.2 Safety population

The Safety Analysis population includes all patients who receive any study medication. Patients will be analyzed according to the treatment that they receive.

3.3 Per Protocol Population

The Per Protocol population includes all randomized patients who receive the full designated amount of study medication according to the correct treatment assignment, who have results from HBV serology and viral markers at baseline and Day 85.

3.5 Screening Failures

Screen failure patients will be defined and a listing, including number identification, demography and why considered a screening failure will be created. In addition, the listing will provide information for rescreening patients.

4. STUDY ENDPOINTS AND DERIVED VARIABLES

This section is intended to outline the way to build the variables needed to assess all study endpoints and state definitions properly. For the statistical methods that will be used, refer to section 5.

4.1 Baseline and demographics characteristics

Baseline was defined as the most recent, non-missing value prior to or on the first study treatment dose date. Demographic data and baseline characteristics will be recorded during Screening. Patients can be re-screened and, in this case, these data at re-screening will be recorded and reassessed.

Specific disease variables are the following: Fibroscan, hepatitis B genotype, HCV, HDV, and HIV tests and HBV serology and viral markers including HBsAg, anti-HBs, HBV DNA, pg-RNA, HBcrAg, HBeAg, HBeAg antibody.

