8.3.4. Height, Weight and BMI

Height and weight will be measured and BMI calculated and recorded at Screening. Weight and BMI will also be recorded at end of the Treatment Period (Day 169 or ET) and at the end of the Follow-up Period (Day 505 or ET).

8.3.5. **Physical Examination**

Physical examinations will be performed by trained medical personnel. A complete physical examination will be performed at Screening and the end of the Treatment Period (Day 169 or ET). Targeted and symptom-driven physical examinations will be performed at all other study visits. Any clinically relevant change in physical examination findings will be recorded as AEs.

8.3.6. **Vital Signs**

Vital signs, including sitting blood pressure, pulse rate (after at least 5 minutes rest), and body temperature, will be recorded at every study visit. Patients will stay in the unit for at least 2 hours following administration of the first and second doses. Vital signs will be assessed before dosing and every 15 minutes post dosing over 2 hours at these two visits. At visits with laboratory assessments, vital signs should be measured before any blood sample collection. Any clinically relevant change in vital signs will be recorded as AEs. Significant changes of vital signs, including the occurrence of tachycardia, bradycardia, hypertension, hypotension and fever will categorized and graded according to the FDA Guidance for Industry: Toxicity Grading Scale for Healthy Adult and Adolescent Volunteers Enrolled in Preventive Vaccine Clinical Trials [United States Food and Drug Administration 2007].

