10. STATISTICS

10.1. General Procedures

Baseline is defined as data collected closest to randomization prior to any study medication dosing. All analyses and summary statistics will be presented by treatment group (HepTcell, placebo).

Descriptive statistics, including the numbers and percentages for categorical variables and the numbers, means, standard deviations, medians, minimums and maximums for continuous variables will be provided by treatment.

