10.6. Statistical Analysis Plan

A formal statistical analysis plan (SAP) will be developed and finalized prior to the database lock and unblinding of treatment assignment. This plan will confirm the analysis sets used in the analysis, outline all data handling conventions, and specify all statistical methods to be used for all safety and efficacy analyses. The SAP will be formalized and signed-off on prior to the locking of the database and unblinding of the treatment codes. The SAP will supersede the protocol with respect to analyses specified, although the primary analysis will remain the same. It is anticipated that analyses other than those specified in the protocol may be pre-specified in the SAP.

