5.3.3.2 Adverse events

AEs will be coded using MedDRA v25.1 or subsequent.

Summary of AEs:

The primary focus of AE reporting will be on Treatment-Emergent Adverse Events (TEAEs). A TEAE is defined as an AE that starts or worsens on or after the date and time of the first administration of the study drug.

All reported AEs (regardless of TEAE or not) will be included in a by-patient AE listing, identifying which is treatment emergent and which it not.

If an AE date/time of onset (occurrence, worsening, or becoming serious) is incomplete, an imputation algorithm will be used to classify the AE as treatment-emergent or not. The algorithm for imputing date/time of onset will be conservative and will classify an AE as treatment-emergent unless there is definitive information to determine it is pre-treatment or post-treatment. Details on classification of AEs with missing or partial-onset dates are provided in Section 5.3.9.

AE summaries will include number (n) and percentage (%) of patients experiencing an AE within each treatment arm and overall if appropriate. The denominator for computation of percentages is the number of patients in the safety population within each treatment arm. The number of events will be included in some summaries as well whenever appropriate.

Unless otherwise specified, when applicable, sorting order will be by decreasing number of patients in PTs within SOCs based on total patients. When more than one PT has same number of patients, the order of presentation will be alphabetical in PTs.

Multiple occurrences of the same event in the same patient will be counted only once for patients counting in the tables within a treatment arm.

Summary of All TEAEs:

The following TEAE summaries will be generated for the safety population:

- An overview of TEAEs. Number (%) of patients will be provided by treatment arm, to include:
 - o TEAEs.
 - o MAEs.
 - o Grade 3 (Severe), Grade 4 (Life-threatening), and Grade 5 (Fatal) TEAEs.
 - Serious TEAEs.
 - Treatment-related AEs (defined as those events other than 'Unrelated/Unlikely related' as assessed by the investigator).
 - TEAEs serious leading to death.
 - TEAEs leading to study drug permanent discontinuation.

22-Apr-2024

- TEAEs leading to clinical management of the AE.
- All TEAEs by primary SOC and PT.
- All TEAEs presented by PT.
- All treatment-related AEs presented by primary SOC and PT.
- All treatment-related AEs Grade 3 or higher, presented by primary SOC and PT.

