5.3.3.11 Vital Signs and Height, weight, and BMI

A summary of vital signs (including systolic and diastolic blood pressure and body temperature (in °C), heart rate and respiratory rate) including change from baseline (where appropriate), presented by descriptive statistics, will be displayed by treatment arm and overall, for each visit day from baseline through Day 169. Particularly, for vital signs measured after first and second doses, the maximum value among all values recorded in the 2 hours post-dosing will be taken as the representative for that day in summaries by visit.

Vital Signs data during the treatment period will be summarized in the current visits: Day 1, 8, 29, 36, 57, 85, 113, 141 and 169. Visits Day 64, Day 92, Day 120 and Day 148 for collection of Vital Signs data during the treatment period were removed in the protocol version for which this SAP version is planned.

For patients following previous versions of the protocol, data recorded on the days of the current visits listed above will be used for analyses. Only if there is no data collected in these visits and these patients have additional values in visits previously collected, those data will be used for analyses following the correspondence: Day 64 to Day 85; Day 92 to Day 113; Day 120 to Day 141; Day 148 to Day 169.

In addition, a summary and change from pre-dose of the values measured in the 2 hours post-dose (at 15 minutes intervals) after the first and second doses will be presented using the maximum value among

all values recorded in the 2 hours post-dosing. Pre-dose will be the latest assessment prior to the dose being summarized.

Height, weight, and BMI and the corresponding change from baseline will be summarized for visits after baseline.

Only available data will be used, and missing data will not be imputed. Change from baseline and predose will be calculated only for patients with non-missing values for both the baseline or pre-dose and the time-point of interest and will be missing otherwise.

Vital Signs (on dosing and no-dosing days) and height, weight and BMI after baseline will be listed.

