14.3.4.1.3	Summary of Clinical Laboratory Hematology Results: Shift from baseline vs post-baseline category	Safety Population	Yes (Through D169)	
14.3.4.2.1	Summary of pre-dose Values and Change from baseline for Clinical Laboratory Biochemistry Results	Safety Population	Yes (Through D169)	
14.3.4.2.2	Summary of Abnormalities for Clinical Laboratory Biochemistry Results	Safety Population	Yes (Through D169)	
14.3.4.2.3	Summary of Clinical Laboratory Biochemistry Results: Shift from baseline vs post-baseline category	Safety Population	Yes (Through D169)	
14.3.4.3.1	Summary of pre-dose Values for Continuous Urinalysis Results	Safety Population	Yes	
14.3.4.3.2	Summary of Values for Categorical Urinalysis Results	Safety Population	Yes	

TFL Number	Title	Analysis Set	Included in	TOP LINE
			Final report	TABLES
14.3.4.3.3	Summary of Abnormalities for Clinical Laboratory	Safety Population	Yes	
	Urinalysis Results			
14.3.4.3.4	Summary of Clinical Laboratory Urinalysis Results:	Safety Population	Yes	
	Shift from baseline vs post-baseline category			
14.3.5 Reactoger	-			
14.3.5.1	Incidence of Reactogenicity Events	Safety Population	Yes	
14.3.6 Hepatitis F	Flares			
14.3.6.1	Incidence of Hepatitis Flares	Safety Population	Yes	
14.3.6.2	Summary of patients achieving HBsAg loss by Hepatitis Flares	Safety Population	Yes	
14.3.6.3	Logistic Regression Analysis for HBsAg loss by Hepatitis Flares at Day 169	Safety Population	Yes	
14.3.7 Vital Signs	5		,	I
14.3.7.1	Summary of Values and Change from baseline for Vital Signs: Results by Visit	Safety Population	Yes (Through D169)	
14.3.7.2	Summary of Values and Change from pre-dose for Vital Signs: Results after first and second dose	Safety Population	Yes (Through D169)	
14.3.7.3	Summary of Height, weight, and BMI change from baseline	Safety Population	Yes (Through D169)	
14.3.8 Electrocar	diogram Measurements (12-Lead ECG)			
14.3.8.1	Summary of Evaluation for 12-Lead ECG Results	Safety Population	Yes (Through D169)	
14.3.9 Physical E	xamination		,	
14.3.9.1.1	Complete Physical Examination after Baseline (Day 169/ET)	Safety Population	Yes	
14.3.9.1.2	Targeted and symptom-driven Physical Examination after Baseline	Safety Population	Yes (Through D169)	
Listing Number	Examination and Basonile			
16.2.1 Patient's D	Disposition			

22-Apr-2024

TFL Number	Title	Analysis Set	Included in	TOP LINE
			Final report	TABLES
16.2.1.1	Listing of Patient's Disposition and Status	All Patients in DB	Yes	

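### The SAP baseline rule cuts off at the first dose date, not the dose time, so read literally it makes a post-dose Day 1 reading the vital-sign baseline in the baseline summary and Table 14.3.7.1

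*SAP*

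**What the plan says.** The SAP's general definition, in section 4.1, is: "Baseline was defined as the most recent, non-missing value prior to or on the first study treatment dose date". The protocol's, in section 10.1 and again in the study summary, is: "Baseline is defined as data collected closest to randomization prior to any study medication dosing".

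Protocol 8.3.6 (and 6.3) sets the readings for the Dose 1 and Dose 2 visits: "Vital signs will be assessed before dosing and every 15 minutes post dosing over 2 hours at these two visits".

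SAP 5.3.3.11 plans two vital-sign summaries. One is by visit with change from baseline, listed as Table 14.3.7.1: "Summary of Values and Change from baseline for Vital Signs: Results by Visit". In it, the Dose 1 and Dose 2 days are represented as follows: "the maximum value among all values recorded in the 2 hours post-dosing will be taken as the representative for that day in summaries by visit". The other, Table 14.3.7.2, reports change from pre-dose after Doses 1 and 2, and for that purpose "Pre-dose will be the latest assessment prior to the dose being summarized".

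On precedence, Protocol 10.6 states: "The SAP will supersede the protocol with respect to analyses specified, although the primary analysis will remain the same". SAP 5.3.17, which records changes from the protocol's planned analyses, mentions only the ECG parameters.

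**The concern.** The two definitions agree for anything measured once on Day 1 before the injection. They part where a measurement is repeated on that day after dosing, and vital signs are scheduled that way in every dosed patient. The latest value on the first dose date is then a reading taken after exposure.

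A change from baseline in a safety table is meant to compare a patient with their own unexposed state. If the reference is already post-injection, a sustained early rise in temperature or pulse becomes part of the reference. It drops out of the Day 1 change and makes later visits look lower than they are. Because the SAP takes precedence for everything but the primary analysis, its looser rule would govern this table, and the departure from the protocol is not declared.

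**Working it through.** The plan reports no figure that depends on this rule, so there is nothing to reproduce. The check applies both rules to the scheduled Day 1 readings and follows the consequence.

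1. **Number of readings.** Post-dose readings on the first dose date: 120 min / 15 min = 8, the last at about +120 minutes, plus one pre-dose reading.

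2. **Which reading each rule picks.** The SAP rule takes the latest value dated no later than the dose date, which is the reading at about +120 minutes. The protocol rule excludes everything after dosing, which leaves the Day 1 pre-dose reading.

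3. **Whether another section overrides this.** The pre-dose definition in SAP 5.3.3.11 serves the change-from-pre-dose summary. The same section speaks of baseline and pre-dose as alternative references, so it does not redefine baseline for Table 14.3.7.1. SAP 5.3.1.8, on baseline vital signs, contains no time rule. Elsewhere the SAP does use time: "A TEAE is defined as an AE that starts or worsens on or after the date and time of the first administration".

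4. **Algebra.** Write a patient's deviations from their usual level as e₀ for the pre-dose reading, d + eᵢ (i = 1 to 8) for the post-dose readings and e_L for a later non-dosing visit, where d is a shift sustained over the 2 hours. Day 1 is represented by the post-dose maximum.
   - Day 1 change, protocol rule: d + max(eᵢ) − e₀.
   - Day 1 change, SAP rule: (d + max(eᵢ)) − (d + e₈) = max(eᵢ) − e₈. The shift d has gone, and the result cannot be negative because e₈ is one of the values in the maximum.
   - Later change, protocol rule: e_L − e₀, with mean 0.
   - Later change, SAP rule: e_L − (d + e₈), with mean −d.

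5. **Numbers.** The documents give neither d nor a standard deviation, so both are assumed. With independent normal readings, SD 5 and 100,000 simulated patients per row, the mean changes are:

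| Assumed d | Day 1, protocol rule | Day 1, SAP rule | Later visit, protocol rule | Later visit, SAP rule |
|---|---|---|---|---|
| 0 | 7.12 | 7.10 | 0.03 | 0.02 |
| 2 | 9.12 | 7.12 | 0.02 | −1.98 |
| 5 | 12.15 | 7.13 | 0.02 | −5.00 |
| 10 | 17.11 | 7.10 | −0.01 | −10.02 |

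The smallest simulated Day 1 change under the SAP rule was 0.00. With SD 8 the Day 1 mean under the SAP rule stays between 11.34 and 11.40 whatever d is, and the later-visit means are 0.00, −2.06, −5.04 and −10.02. The bias simply returns the assumed shift. The table shows direction and mechanism and is not an estimate for this trial.

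**The case against.** The strongest reply is that the acute window is already covered. Table 14.3.7.2 measures the 2-hour maximum after Doses 1 and 2 against a true pre-dose value. Protocol 8.3.6 has significant vital-sign changes, including fever and tachycardia, graded on a toxicity scale, and clinically relevant changes recorded as adverse events. Temperature is also kept in a daily diary for 7 days after each dose, with fever a solicited event, and all vital signs are listed. This stands: one might infer that an early reaction would go unseen, and the documents do not support that.

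A second reply is that the SAP is only ambiguous. Section 4.1 goes on to say that baseline characteristics are recorded at Screening, and 5.3.1.8 uses the re-screening visit for re-screened patients. Section 5.3.3.12 gives the laboratory pre-dose window for Dose 2 as ending on the dose date, so the authors may use a date to mean pre-dose. This stands in part. A careful programmer might choose the pre-dose record. But the re-screening sentence settles which screening visit counts, not which Day 1 reading, and a date cut-off works for laboratory tests only because no post-dose repeat is scheduled that day. Nothing tells the programmer to depart from the stated rule for vital signs.

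A third reply is that the fault does not spread to other Day 1 data. This also stands. The schedule of events has a single Day 1 entry each for safety laboratory tests, virology and PBMC, with no post-dose repeat.

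**Conclusion.** The point holds within narrow limits. SAP 4.1 conflicts with Protocol 10.1, and read literally it selects a post-dose reading as the vital-sign baseline for any patient with a non-missing post-dose reading on Day 1. It affects two descriptive safety outputs: the baseline vital-sign summary and Table 14.3.7.1. The bias in later-visit changes is the negative of the mean shift at the last Day 1 reading. If that shift differs between arms, the between-arm contrast is biased by the negative of the difference. The shift is unknown, and if it is zero no bias arises at later visits.

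A reader might infer that the efficacy baselines, including the primary endpoint's qHBsAg, are contaminated too. The documents do not show this, since one Day 1 virology sample is scheduled. Nor do they show that the tables were actually produced from post-dose readings; they show only that the written rule calls for it.

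**What to change.** In SAP 4.1, define baseline as the last non-missing value before the date and time of first dose and, where the time is missing, use the record labelled as the scheduled pre-dose assessment. This restores agreement with Protocol 10.1.

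The text change is one phrase, plus the matching line in the derivation program. Some rework may follow. SAP version 2.0 was written after the Week 24 interim analysis, and its addendum of supplementary outputs contains no vital-sign summary table, so Table 14.3.7.1 has probably been produced already. The sponsor should confirm which Day 1 record served as baseline. If it was the pre-dose record, a clarifying note is enough. If it was post-dose, rerun Table 14.3.7.1 and the baseline vital-sign summary. No new data are needed, because the pre-dose reading is already scheduled.

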4.2 Efficacy endpoints

4.2.1 Primary Efficacy Endpoint

The proportion of patients achieving virologic response, defined as a 1.0-log reduction in quantitative HBsAg (qHBsAg) or serologic clearance of HBsAg, Baseline to Day 169.

A patient is considered to have achieved the virologic response if one of the following occurs:

1.- Log reduction in qHBsAg of at least 1.0, where

Log reduction = log₁₀ (A/B), where A= qHBsAg at Baseline and B= qHBsAg to Day 169

2.- Serologic clearance of HBsAg is achieved on Day 169:

HBsAg to Day 169 is below the limit of quantitation (defined as 0.05 IU/mL).

Please refer to section 5.3.2 for details on the handling of intercurrent events and missing data.

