4. STUDY PLAN

4.1. Study Design

This is a Phase 2, randomized, double-blind, placebo-controlled, multicenter clinical trial to evaluate the antiviral effects, immunogenicity, and safety of HepTcell in treatment-naïve patients with inactive CHB and low HBsAg levels (10 to 200 IU/mL).

After providing written informed consent, patients will undergo a screening period of up to 35 days. A Fibroscan will be performed in all patients who have not had this examination within the previous 12 months before Screening with the exception of patients with a prior history of liver biopsy within the past 2 years demonstrating no evidence of significant fibrosis.

Patients who meet inclusion and exclusion criteria will be randomized in a 1:1 ratio to receive 6 IM doses of HepTcell or placebo (normal saline) at study visits 4 weeks apart (Days 1, 29, 57, 85, 113, 141). Randomization may occur up to 3 working days before the first day of dosing to allow for the possible preparation of study medication by a central pharmacy and shipment to the study site. Adverse events (AEs) will be monitored, and blood samples will be collected for qHBsAg, anti-HBs, HBV DNA, HBV pg-RNA, HBcrAg, and IFN-γ ELISpot assay in PBMCs. Patients will record any reactogenicity events (see Appendix 1) for 7 days after each administration of study medication in a diary. A visit consisting of a targeted physical examination and safety laboratory tests, including liver panels, will be conducted 7±2 days after administration of Doses 1 and 2 of study medication. These visits, per the Schedule of Events (Table 1 and Table 2), may be conducted at home or workplace or, in part, as a telemedicine visit, at the discretion of the Investigator.

If the patient has experienced an acute illness or temperature > 38°C in the 2 days prior to dosing, the administration of study medication and corresponding visit will be delayed until the illness or fever has resolved.

A Safety Committee will conduct regular blinded reviews of all AEs and reactogenicity events. The safety of study participants will also be overseen by an unblinded Data Monitoring Committee (DMC); its responsibilities will be laid out in a DMC charter.

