4.4. Rationale for Study Population

Patients with inactive CHB and low HBsAg are likely to represent a population of patients more likely to benefit from immunotherapy than the population in Study FP02.2_CS_01, who could only achieve viral suppression through the use of nucleoside analogues. Inactive CHB patients have relatively low circulating levels of HBV DNA and are already demonstrating intrinsic immune control, albeit incomplete, over the virus. T cell responses against HBV antigens have also been shown to be inversely associated with serum HBsAg level, with lower levels leading to higher rates of spontaneous HBsAg serologic clearance [Loggi 2013]. In two studies of patients with inactive CHB treated with IFN-α therapy, the HBsAg cutoffs predicting HBsAg serologic clearance were 71 and 200 IU/mL, respectively [Lim 2019, Cao 2017]. In a metanalysis

of effects of patients treated with IFN- α , baseline qHBsAg levels predicted functional cure [Song 2021]. After 48 weeks of therapy, the HBsAg clearance rates were 92% (95% CI: 79% - 99%) for HBsAg <10 IU/mL, 88% (95% CI: 77% -95%) for <20 IU/mL, 73% (95% CI: 62% - 83%) for <100 IU/mL, 60% (95% CI: 48% - 71%) for <500 IU/mL, and 39% (95% CI: 25% - 53%) for <1000 IU/mL. While it is clear that clearance of HBsAg is predicted by baseline levels in these studies, there is minimal change in levels between 100 and 500 IU/mL (13%), and the most significant drop-off in HBsAg clearance is in those with qHBsAg >1000 IU/mL (34%). These observations support the recruitment of a well-defined subpopulation of inactive CHB patients with low qHBsAg levels to enhance anti-HBV immune responses and increase HBsAg loss rates. The provision for allowing the participation of patients with any one HBsAg level within the eligible range (qHBsAg \geq 10 IU/mL but \leq 200 IU/mL) within the past 12 months is to account for the variability in the quantitative HBsAg assay.

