5.2. Inclusion Criteria

Patients who meet all of the following inclusion criteria may be included in the study.

- 1. Able and willing to provide informed consent
- 2. Men and women 18 to 65 years of age, inclusive
- 3. Body Mass Index (BMI) 18.0 to 34.9 kg/m², inclusive
- 4. Inactive, treatment-naïve CHB with documented HBsAg positivity for at least 12 months before Day 1. (The history of HBsAg positivity may be reduced to 6 months provided HBV anti-core IgM antibodies are negative).
- 5. qHBsAg ≥ 10 IU/mL but ≤ 200 IU/mL in the 12 months prior to Screening or from informed consent to randomization
 - If a patient has more than one qHBsAg value within 12 months and prior to randomization, the patient will be deemed eligible if any one measurement is within the eligible range.
- 6. AST, ALT, INR, albumin, total bilirubin (excluding patients with Gilbert Syndrome, who will only be eligible for study participation if total bilirubin is ≤ 3.0 mg/dL) and direct bilirubin within normal limits at screening. Note: ALT and AST elevations up to 1.5 x ULN are allowed if evidence of hepatic steatosis, defined as one of the following criteria: 1) fatty liver on ultrasound, or other imaging modality or Fibroscan controlled attenuation parameter (CAP) ≥ 260 dB/m. To qualify under these conditions, HBV DNA must be <2,000 IU/mL, and there must be no history or signs of liver disease other than fatty liver and HBV.
- 7. Negative drug screen at Screening unless prescribed by a medical practitioner for medical use (NB, recreational and prescription cannabis is allowed)
- 8. For women of childbearing potential (women who are not permanently sterile [documented hysterectomy, bilateral tubal ligation, salpingectomy, or oophorectomy] or postmenopausal [12 months with no menses without an alternative medical cause]):
 - a. Negative pregnancy test on Day 1
 - b. Willingness to practice a highly effective method of birth control with low user dependency from screening through one menstrual cycle after the last dose of study medication, which include:
 - i. Abstinence

- ii. Sex only with persons of the same sex
- iii. Monogamous relationship with vasectomized partner
- iv. Intrauterine device
- v. Combined estrogen and progestogen containing hormonal contraception associated with inhibition of ovulation (oral, intravaginal, transdermal)
- vi. Progestogen-only hormonal contraception associated with inhibition of ovulation (oral, injectable or implantable)

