2.3.2. Eligibility criteria

2.3.2.1 Inclusion Criteria

- 1. Able and willing to provide informed consent
- 2. Men and women 18 to 65 years of age, inclusive
- 3. Body Mass Index (BMI) 18.0 to 34.9 kg/m², inclusive
- 4. Inactive, treatment-naïve CHB with documented HBsAg positivity for at least 12 months before Day 1. (The history of HBsAg positivity may be reduced to 6 months provided HBV anti-core IgM antibodies are negative).
- 5. qHBsAg ≥ 10 IU/mL but ≤ 200 IU/mL in the 12 months prior to screening or from informed consent to randomization
 - If a patient has more than one qHBsAg value within 12 months and prior to randomization, the patient will be deemed eligible if any one measurement is within the eligible range.
- 6. AST, ALT, INR, albumin, total bilirubin (excluding patients with Gilbert Syndrome, who will only be eligible for study participation if total bilirubin is ≤ 3.0 mg/dL) and direct bilirubin within normal limits at screening. Note: ALT and AST elevations up to 1.5 x ULN are allowed if evidence of hepatic steatosis, defined as one of the following criteria: 1) fatty liver on ultrasound, or other imaging modality or Fibroscan controlled attenuation parameter (CAP) ≥ 260 dB/m. To qualify under these conditions, HBV DNA must be <2,000 IU/mL, and there must be no history or signs of liver disease other than fatty liver and HBV.

- 7. Negative drug screen at screening unless prescribed by a medical practitioner for medical use (NB, recreational and prescription cannabis is allowed)
- 8. For women of childbearing potential (women who are not permanently sterile [documented hysterectomy, bilateral tubal ligation, salpingectomy, or oophorectomy] or postmenopausal [12 months with no menses without an alternative medical cause]):
 - a. Negative pregnancy test on Day 1
 - b. Willingness to practice a highly effective method of birth control with low user dependency from screening through one menstrual cycle after the last dose of study medication, which include:
 - i. Abstinence
 - ii. Sex only with persons of the same sex
 - iii. Monogamous relationship with vasectomized partner
 - iv. Intrauterine device
 - v. Combined estrogen and progestogen containing hormonal contraception associated with inhibition of ovulation (oral, intravaginal, transdermal)
 - vi. Progestogen-only hormonal contraception associated with inhibition of ovulation (oral, injectable or implantable)

vii. Intrauterine hormone-releasing system

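### The HBsAg-clearance component of the primary endpoint has no baseline condition, so a patient already below 0.05 IU/mL before the first dose would count as a responder with no change on study

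*SAP*

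**What the plan says.** **Endpoint.** SAP 4.2.1 joins two components with an either/or: "A patient is considered to have achieved the virologic response if one of the following occurs". The first is "Log reduction in qHBsAg of at least 1.0, where" the reduction is log10 of baseline over Day 169. The second is "HBsAg to Day 169 is below the limit of quantitation (defined as 0.05 IU/mL"). Only the first uses the baseline value. SAP 4.2.2 defines the secondary HBsAg-clearance endpoint by the same Day 169 test. SAP 5.3.2.1 and 5.3.2.2.1 handle early discontinuation or a missing Day 169 value by looking at the last assessment available before Day 169, again with no baseline condition.

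**Baseline.** SAP 4.1: "Baseline was defined as the most recent, non-missing value prior to or on the first study treatment dose date". This need not be the value that qualified the patient.

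**Eligibility.** The population is described as having "low HBsAg levels (10 to 200 IU/mL") (Protocol 4.1). Criterion 5 asks for "qHBsAg ≥ 10 IU/mL but ≤ 200 IU/mL in the 12 months prior to screening or from informed consent to randomization" (SAP 2.3.2.1). Where there are several values, "If a patient has more than one qHBsAg value within 12 months and prior to randomization, the patient will be deemed eligible if" any one of them is in range (Protocol 5.2). Protocol 4.4 gives assay variability as the reason for "allowing the participation of patients with any one HBsAg level within the eligible range". Criterion 4 asks for a documented history of HBsAg positivity. Exclusion 3 bars a recent 1-log rise in HBsAg but says nothing about a fall. The mITT set (SAP 3.1) needs a baseline but sets no minimum value.

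**The concern.** A response component should record something that happens after randomised treatment starts. The clearance test, as derived, looks at one time point only. The qualifying value may be about 13 months old at Day 1 (12 months before screening plus up to 35 days of screening), so the written rules leave room for a patient whose HBsAg has already gone below the limit by the first dose. That patient would be scored a responder for staying where they began.

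The planned placebo rate is 3%, about one patient in 40, so very few such patients would be enough to raise the placebo rate, dilute the contrast and move the result. Two programmers could also score the same patient differently, one from the derivation and one from the endpoint's wording about achieving clearance from baseline to Day 169.

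**Working it through.** **Inputs.** Clearance limit 0.05 IU/mL and the 1.0-log rule (SAP 4.2.1); eligibility range 10 to 200 IU/mL (SAP 2.3.2.1); 40 per arm, 3% on placebo, 25% on HepTcell, two-sided 0.05, about 80% power (SAP 5.1). The test is Fisher's exact test, as named in Protocol 10.4.1.

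**1. The plan's own figure.** Full enumeration of Fisher's test with 40 per arm, 3% against 25%, gives 78.0% power, in line with the stated figure.

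**2. Where clearance adds a responder.** Let A be baseline and B be Day 169. Clearance needs B < 0.05. If A ≥ 0.5, then A/B > 0.5/0.05 = 10, so the 1-log component is already met. Clearance can therefore add a responder only when A < 0.5. If a result reported as <0.05 is set to 0.04, by analogy with the examples in SAP 5.3.8, the working bound is 0.4.

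**3. Two groups below that bound.**
- *A from 0.05 to 0.5, B below 0.05.* The patient was measurable at baseline and is not at Day 169. This is loss on study, and a 1-log fall may not be measurable so near the assay floor. This is what a clearance component is for.
- *A below 0.05, B below 0.05.* With both set to 0.04, log10(0.04/0.04) = 0. The patient has no change and is a responder through clearance alone. This is the defect.

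**4. How far a patient must fall before dosing.** From the lowest qualifying value, log10(10/0.05) = 2.30. From 200 IU/mL, log10(200/0.05) = 3.60.

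**5. Effect on power.** Let f be the share of each arm below the limit at baseline and throughout. The documents give no f; the values below are assumed. Under the written rule the rates become f + (1 − f) × 0.03 and f + (1 − f) × 0.25. With these patients scored as non-responders they become (1 − f) × 0.03 and (1 − f) × 0.25.

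| f (assumed) | Rates, written rule | Power | Rates, scored as non-responders | Power | Loss due to the rule |
|---|---|---|---|---|---|
| 0% | 3.0% vs 25.0% | 78.0% | 3.0% vs 25.0% | 78.0% | 0 |
| 1% | 4.0% vs 25.8% | 74.4% | 3.0% vs 24.8% | 77.3% | 2.9 points |
| 2.5% | 5.4% vs 26.9% | 69.3% | 2.9% vs 24.4% | 76.3% | 7.0 points |
| 5% | 7.9% vs 28.8% | 61.3% | 2.9% vs 23.8% | 74.4% | 13.1 points |

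The last column is the right measure of the rule. Comparing with 78.0% would also charge it for patients who cannot respond under either rule.

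**6. Sensitivity to one patient.** With 0 of 40 placebo responders, 6 HepTcell responders give p = 0.0255. With 1 of 40, 7 give p = 0.0568 and 8 give p = 0.0289. One extra placebo responder therefore raises the number needed from 6 to 8.

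SAP 5.3.2.1 allows a chi-square test unless most expected counts are small. Under that selection rule the planned power is 88.5% rather than 78.0%, so the power figures and responder thresholds above apply to Fisher's test only.

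**The case against.** **The case is largely shut out by other text.** Criterion 4 can be read as positivity running up to Day 1. HBV serology is drawn at screening and on Day 1, so a negative screening value could be seen before randomization, and eligibility deviations are reviewed before each lock. The endpoint speaks of achieving clearance from baseline to Day 169, which implies a transition. This stands as a reason to expect few such patients. It does not close the gap: Criterion 4 asks for a documented history rather than a positive Day 1 test, and the derivation in SAP 4.2.1, which is what gets programmed, tests Day 169 alone.

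**The size is unknown and may be zero.** This stands. A fall of at least 2.3 log without treatment is a great deal, when the plan expects only 3% of placebo patients to meet the response definition over 24 weeks. The power figures illustrate; they do not estimate.

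**The plan would show the problem.** Baseline viral markers are summarised by arm with minimum and maximum, every value is listed, and a logistic model adjusts for baseline qHBsAg. The summaries and listings would reveal an affected patient, but none of this changes how that patient is scored in the primary comparison.

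**Stronger readings a reader might infer.** One is that every responder added from a baseline below 0.5 IU/mL reflects a fall before treatment. The documents do not support this: from 0.05 to 0.5 IU/mL, clearance happens on study. Another is that the rule favours HepTcell. Patients already below the limit who stay there are expected equally in both arms under randomization, so the expected effect is dilution, although chance imbalance in a few patients could go either way. A third is that the rule affected the Week 24 result. Nothing in the documents shows that any such patient was enrolled.

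**Conclusion.** The point holds in a narrow form. The clearance rule in SAP 4.2.1, repeated for the secondary HBsAg endpoint in 4.2.2, would score a patient who is below 0.05 IU/mL at baseline and stays there as a responder, and no eligibility rule or analysis-set definition expressly keeps such a patient out. It is an error in the rule itself, worth correcting because the primary comparison rests on few responders. Its practical size is probably small. If 1% to 5% of each arm were affected, the rule would cost about 3 to 13 points of power. This assumes equal shares in both arms, the planned rates among the remaining patients, and Fisher's test at two-sided 0.05. If no patient is affected, the cost is nil.

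**What to change.** In SAP 4.2.1 and 4.2.2, and in the last-assessment rules in 5.3.2.1 and 5.3.2.2.1, count HBsAg clearance as a response only when baseline HBsAg is at or above 0.05 IU/mL. Score patients below that at baseline as non-responders, keep them in the denominator, and report their number by arm. Leave clearance from a baseline of 0.05 to 0.5 IU/mL as a response.

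SAP version 2.0 already reports that the Week 24 analysis did not meet the primary endpoint, so label the change as post hoc and show the primary and secondary results under both rules. If no patient had a baseline below 0.05 IU/mL, saying so settles the matter.

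A table restricted to baseline qHBsAg of 10 to 200 IU/mL is optional and supportive only, because it would also drop patients whom Protocol 4.4 admits on purpose.

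The cost is one clause, one count by arm and a second set of results. The downside is that the few affected patients can no longer count as responders.
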